8.3.1. Health Care Cost and Utilization

All cost and utilization measures will be identified in the 12-month pre-index period and the 12- month post-index period. Claims occurring on the index date will be considered part of the post-index period. Baseline and follow-up costs and the change in 12-month costs from baseline to follow-up will then be examined. Cost measures will comprise the total amount paid by the health plan and patient.

• All-cause health care resource utilization- Medical resource utilization will be calculated for outpatient visits, emergency department (ED) visits, and inpatient admissions and pharmacy utilization will include all paid prescription claims.

• RA-related resource health care utilization.

- Medical resource utilization related to RA will be calculated for outpatient visits, ED visits, and inpatient admissions with an RA diagnosis in any claim position.
- RA-related treatment administrations (with and without a concurrent RA diagnosis) will also be identified by presence of HCPCS codes for ADA, ETN, other TNFI and other advanced therapy; methotrexate or other NB-DMARD; low, medium and high potency orticosteroids; NSAIDS; and strong and weak opioids (*See Appendices Appendix 1, Appendix 2, Appendix 5*).
- Pharmacy utilization will included all paid prescription claims for TOFA, ADA, ETN, another TNFI or alternative MOA; methotrexate, sulfasalazine, leflunomide, hydroxychrolorquine and other NB-DMARDs; low, medium, high potency corticosteroids; NSAIDS; and weak and strong opioids (*See Appendices Appendix 1, Appendix 2, Appendix 5*).

- Health care costs-Health care costs will be computed as the combined health plan and patient paid amounts. Costs will be calculated as total costs, pharmacy/treatment costs, and medical costs. Medical costs will be further broken down into outpatient costs, emergency room costs, and inpatient costs. Costs will be adjusted using the annual medical care component of the Consumer Price Index (CPI) to reflect inflation between 2014 (the earliest start of the pre-index period) and 2017 (the cost of claims occurring in 2018 will not be adjusted).¹⁶
- Costs from other payers are of importance for older patients dually eligible for commercial and Medicare coverage. Payments from Medicare (and other payers) will be estimated based on coordination of benefits information obtained by the health plan in its usual course of business. This study will incorporate the amounts estimated to be paid by other payers for a total paid or allowable amount.¹⁷
- All-cause health care costs- calculated as total of medical (outpatient, inpatient and ED) visits regardless of reason and all prescription costs.
- **RA-related health care costs-** RA-related health care costs will be calculated as total medical and treatment costs related to RA.
 - RA-related medical costs will include costs for outpatient, inpatient and ED vists with an RA diagnosis in any claim position
 - For outpatient visits with an RA diagnosis and administration of an RArelated treatment (see below), the non-administration costs will be characterized as part of RA-related Medical costs and the administration costs will be part of RA-related Treatment costs below.
 - Outpatient visits without an RA diagnosis, but with administration of an RArelated treatment will not be included in the RA-related Medical costs, but will be evaluated for administration costs as part of RA-relatedTreatment costs below.

Note: given variability in capture of HCPCS codes in inpatient setting across databases, RA- related treatement costs are limited to outpatient visits only.

- RA-related treatment costs will include the cost of:
 - outpatient administration of bDMARDs, NB-DMARDs, corticosterioids, NSAIDS, and opioids based on HCPCS codes regardless of RA diagnosis on claim, AND,
 - cost of prescription fills for TOFA/ADA, ETN, other advanced therapies, NB-DMARDs, corticosterioids, NSAIDS, and opioids.

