7.2. Secondary Objectives

To compare patients with (1) high (>median) vs. low (≤median) TOFA index prescription OOP costs, and, (2) TNFi cycling with ETN and ADA vs. switching to TOFA on:

- Differences in demographic and clinical characteristics;
- Treatment patterns including dosing, concomitant medication use, adherence, and switching, and a 6-factor effectiveness proxy (ie, Curtis algorithm) between comparator cohorts;
- Post-index and change (Post-Pre) in All-cause and RA-related health care utilization associated costs.

C

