8.2. Setting

This study will leverage the de-identified, insurance claims database Truven Health MarketScan, between January of 2012 and September 2017. The database is further described in Section 8.4.

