8.2.1. Inclusion Criteria

Patients must meet all of the following inclusion criteria to be eligible for inclusion in the study:

- 1. The **first pharmacy claim for TOFA and then ETN or ADA** between Jan 2014 and Sep 2016 represents the index claim *(See Appendix 1 for codes)*. Selection of comparator groups will be hierchical per the following:
 - a. First, select patients receiving ≥1 tofacitinib (TOFA) pharmacy claim (Jan 2014–Sep 2016) who did not have a TOFA claim anytime prior to index.
 - b. Amongst remaining patients, select those receiving ≥1 ETN or ADA pharmacy claim, assign per whichever occurs first, over same time period (Jan 2014-Sep 2016) who did not have a respective pharmacy or administration claim for index medication anytime prior to index.
- 2. Patients do have >1 advanced therapy filled on index date.

- 3. Physician diagnosis of RA (in any position) during the 1-year pre-index period, or on the index date:
 - ICD-9 = 714.0x-714.4x, 714.81;
 - ICD-10 = M05.x, M06.0–M06.3, M06.8–M06.9.
- 4. Patients don't have claims for other conditions for which TOFA and/or advanced therapies are used, during the anytime pre-index period or on the index date.

Disease	ICD-9 diagnosis code	ICD-10 diagnosis code
Ankylosing Spondylitis	720.0x	M45.0 - M45.9
Crohn's Disease	555.xx	K50.*
Psoriasis	696.1x	L40.0*-L40.4*, L40.8*-L40.9*
Psoriatic Arthritis	696.0x	L40.5*
Ulcerative Colitis	556.xx	K51.*

Table 1. Exclusionary Diagnoses

- 5. Commercially insured or Medicare beneficiaries at index.
- 6. Continuous enrollment during 1 (360 days)-year pre- (pre-index period) and 1-year post- index.
- 7. Age 18+ years at index.
- 8. Study cohorts.
 - a. TOFA Advanced Therapy Naïve OOP Cost Cohort.
 - Identify those with no advanced therapy (bDMARDs/JAK inhibitors) anytime before index TOFA prescription.
 - b. ETN or ADA to TOFA OOP Cost and TNFi Cycling Cohort.
 - Identify those that had ADA or ETN, but not both, and no other advanced therapy anytime pre-index TOFA (*See Appendix 1*).
 - c. ADA to ETN TNFi Cycling Cohort.

- In those newly starting ETN, patient must have a claim for ADA and no other advanced therapy (*See Appendix 1*), including index ETN (pharmacy/admin claims), anytime pre- index ETN.
- d. ETN to ADA TNFi Cycling Cohort.
 - In those newly starting ADA, patient must have a claim for ETN and no other advanced therapy (*See Appendix 1*), including index ADA (pharmacy/admin claims), anytime pre- index ADA.

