For this objective descriptive and multivariable analysis will be conducted. For the descriptive analysis, 12-month pre- and post-index cost measures will be presented per patient during the baseline and follow-up. The change in 12-month costs from the baseline to the follow-up will also be calculated. In addition, total all-cause cost will be presented in each of the months of the baseline and follow-up. The mean cost in each month will be included on a figure demonstrating the trend in costs over time. Multivariable analysis of follow-up health care cost will also be conducted using generalized linear models (see Section 8.7.4).

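### The CPI rule starts in 2014 but pre-index costs reach back to January 2013, so 2013 claims have no stated adjustment and the post-minus-pre cost change could be modestly overstated

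*Combined protocol and SAP*

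**What the plan says.** Section 8.3.1 adjusts costs with the yearly medical-care CPI for inflation "between 2014 (the earliest start of the pre-index period) and 2017 (the cost of claims occurring in 2018 will not be adjusted". The same section fixes the cost windows: "All cost and utilization measures will be identified in the 12-month pre-index period" and in the 12 months after it, with the index date counted as post-index.

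The dates come from elsewhere in the protocol:

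- Section 8.2.1, criterion 1: the first qualifying pharmacy claim "between Jan 2014 and Sep 2016 represents the index claim".
- Section 8.2.1, criterion 6: "Continuous enrollment during 1 (360 days)-year pre- (pre-index period) and 1-year post- index".
- Section 8.2: the database is used "between January of 2012 and September 2017".

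The adjusted costs feed a secondary objective in Section 7.2, "Post-index and change (Post-Pre) in All-cause and RA-related health care utilization associated costs". For this, Section 8.7.2.4 plans a descriptive change score ("The change in 12-month costs from the baseline to the follow-up will also be calculated") and a monthly plot ("The mean cost in each month will be included on a figure demonstrating the trend in costs over time").

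**The concern.** 2014 is the first index year, not the first pre-index year. Patients indexed during 2014 have part or all of their baseline costs in 2013, and the stated span gives no factor for that year. Three implementations are possible: extend the CPI series to 2013, give 2013 claims the 2014 factor, or leave them nominal.

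The last two err in one direction. Only the pre-index side contains 2013 claims, so baseline cost comes out too low and the signed change too high: a rise looks larger, and a fall looks smaller. The monthly plot would also show a small artificial climb before index, because the earliest baseline months hold most of the 2013 claims.

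The other end of the rule does not fit the study either. No study claim can fall in 2018, yet exempting 2018 claims hints at 2018 dollars while the stated span ends in 2017. Two programmers could reasonably produce different dollar years.

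**Working it through.** **The plan's own figure.** Section 8.3.1 gives 2014 as the start of the pre-index period. From the earliest index date:

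- 1 Jan 2014 − 12 months = 1 Jan 2013
- 1 Jan 2014 − 360 days = 6 Jan 2013

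The two-year enrollment mentioned in Section 8.9 would move the start further back, to January 2012. No variant gives 2014. At the other end, 30 Sep 2016 plus one year falls no later than 30 Sep 2017, so the 2018 clause has nothing to act on.

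**Share of baseline time in 2013.** The index window, January 2014 to September 2016, is 33 months. Assume index dates are spread evenly over it.

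- 2014 starters: on average half the pre-index year, 0.5
- 2015–2016 starters: 0
- All patients: 0.5 × 12/33 = 18.2%

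A day-by-day count over all 1,004 possible index dates with a 360-day window gives 0.4945 and 0.180.

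**Size of the understatement.** The documents give no CPI values, so yearly medical inflation *i* is assumed at 2–4%, with flat real cost. The shortfall on a 2013 claim is 1 − (factor used)/(correct factor). Multiplying by the 2013 share gives the shortfall in mean pre-index cost:

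| Treatment of 2013 claims | Shortfall on a 2013 claim | 2014 starters (× 0.5) | All patients (× 0.182) |
|---|---|---|---|
| CPI series extended to 2013 | 0% | 0% | 0% |
| Given the 2014 factor | 1 − 1/(1+i) = 2.0–3.8% | 1.0–1.9% | 0.4–0.7% |
| Left nominal, 2017 dollars | 1 − 1/(1+i)^4 = 7.6–14.5% | 3.8–7.3% | 1.4–2.6% |
| Left nominal, 2018 dollars | 1 − 1/(1+i)^5 = 9.4–17.8% | 4.7–8.9% | 1.7–3.2% |

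In 2017 dollars, per 10,000 dollars of correctly adjusted mean pre-index cost, the mean change over all patients is too high by 0, about 40–70, or about 140–260 dollars.

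**Sensitivity to the cost trend.** If real cost doubles linearly over the pre-index year, the 2013 share for 2014 starters is (1/2 + 1/6)/1.5 = 0.444, or 0.444 × 12/33 = 16.2% overall. The nominal reading in 2017 dollars then gives 3.4–6.5% (1.2–2.3% overall), and the 2014-factor reading 0.9–1.7% (0.3–0.6%).

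**Monthly plot.**

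- Month −12: 11.5/33 = 34.8% of patient time is in 2013. The mean is low by 0.348 × 7.6–14.5% = 2.7–5.1% if nominal, or 0.348 × 2.0–3.8% = 0.7–1.3% with the 2014 factor.
- Month −1: 0.5/33 = 1.5%, so the mean is low by at most 0.2%.

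**Between-cohort contrast.** With equal baseline cost, each 10-point difference between cohorts in the share of 2014 starters shifts the difference in change by 0.10 × 3.8–7.3% = 0.4–0.7% of pre-index cost if nominal, or 0.10 × 1.0–1.9% = 0.1–0.2% with the 2014 factor. Equal index-year mix and equal baseline cost give no shift.

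**The case against.** The best defence is that the sentence does not exempt 2013 claims. It says costs will be adjusted, and the only group it excludes is 2018 claims. Its parenthesis shows that the span was meant to cover the whole pre-index period. A programmer following that purpose would extend the CPI series to 2013, and the error would be zero. Nothing in the text suggests giving 2013 claims the 2014 factor. The affected outcome is secondary and descriptive, no separate cost analysis of 2014 starters is planned, and nothing in the documents shows that cohorts differ in index-year mix.

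Most of this stands as a limit on size. The zero-error reading is plausible, the 2014-factor row is only a possible programming outcome, and the contrasts between cohorts may barely move. It does not rescue the sentence. The written start year is wrong, no other section corrects it, and both readings that keep it bias a named outcome in the same direction. Section 8.8 has analyses programmed to the protocol's specifications, so a second programmer checking against the same sentence could confirm the error.

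**Conclusion.** The concern holds. That the pre-index cost window opens in January 2013 rather than 2014, and that no cost claim can fall in 2018, follows from the protocol's dates without any assumption.

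The consequence is conditional and modest: from nothing, if the CPI series is extended, to a low-single-digit percentage of mean pre-index cost, if 2013 claims stay nominal. That range rests on even index dates, the assumed inflation and the assumed cost trend, and it scales directly with the true share of patients indexed in 2014.

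The reach is confined to baseline costs, the change scores and the pre-index part of the monthly plot. All follow-up claims fall in 2014–2017, so the outcome of the follow-up cost GLM is unaffected; a small indirect effect is possible only if baseline cost enters as a covariate. Persistence does not use costs. This should be corrected, but it does not threaten the study's main conclusion.

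**What to change.** In Section 8.3.1, change the start year to 2013, name one dollar year for all claims and delete the 2018 clause. 2017 is a natural choice because the data end that year, though any single named year would do. Suggested wording:

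> Claims from 2013 through 2016 will be inflated to 2017 US dollars using the annual medical care CPI; claims from 2017 will enter unadjusted.

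The cost is one sentence and one more CPI year in the program. The 2013 claims are already in the data extract, and no patients are lost. Version 1.1 is dated 7 October 2019, after the planned final report date of 30 September 2019, so cost outputs may already exist. In that case, check which factor was applied to 2013 claims. If they were left nominal or under-adjusted, re-run the pre-index costs, the change scores and the monthly plot.

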8.4. Data Source

8.4.1. Truven MarketScan Research Database

The Truven Health MarketScan Research Databases reflects the combined healthcare service use of individuals covered by Truven Health clients (including employers, health plans, and hospitals) nationwide. Truven Health builds databases comprise the healthcare experience of the clients' covered populations, as well as information about the populations themselves and the providers that serve them. MarketScan Research Databases provide detailed cost, utilization, and outcomes data for healthcare services performed in both inpatient and outpatient settings. In the claims databases, the medical services are linked to outpatient prescription drug claims and person-level enrollment data using unique enrollee identifiers.

The MarketScan Commercial Database contains the healthcare experience of privately insured individuals. Coverage is provided under a variety of fee-for-service, fully capitated, and partially capitated health plans, including preferred provider organizations, point of service plans, indemnity plans, and health maintenance organizations.

The data that make up the Commercial Database are stored in the following tables:

- *The Inpatient Admissions Table* contains records that summarize information about a hospital admission. Truven Health constructs this table after identifying all of the service records associated with an admission (eg, the hospital claims, physician claims, surgeon claims, and claims from independent labs). Similar information (such as payments for professional services) is then summed across the claims. The admission record includes the principal procedure and diagnosis, Major Diagnostic Category, and Diagnosis-Related Group. It also includes all diagnoses and procedures (up to 14 each) found on the service records.
- *The Inpatient Services Table* contains the individual claims that are summed to create the inpatient admission records. An admission identifier on both the Inpatient Admissions and the Inpatient Services Tables identifies the claims that make up each admission record.
- *The Outpatient Services Table* comprises services that were rendered in a doctor's office, hospital outpatient facility, or other outpatient facility.
- *The Facility Header Table* contains the header records from facility claims for inpatient and outpatient services, including full diagnosis information.
- *The Outpatient Pharmaceutical Claims Table* contains outpatient prescription drug data from multiple sources, including mail-order data. Each record includes National Drug Code (NDC), therapeutic class, ingredient cost, dispensing fee, copayment, deductible, total gross payment, and other data elements.

- *The RED BOOK[™] Supplement Table* contains *RED BOOK* variables that enhance prescription drug analyses. These variables are linked to the Outpatient Pharmaceutical Claims Table by NDC.
- *The Annual Enrollment Summary Table* provides a single record per year for each enrollee, showing enrollment start and end dates and, for some demographic variables, the most prevalent demographic and plan information; for other variables, monthly values are included.
- *The Enrollment Detail Table* provides a single record per month of enrollment for each enrollee, with detailed demographic information.
- *The Population Aggregate Table* provides average counts of the covered (insured) population to use for rate-supported analysis. The counts are recorded by several demographic variables (eg, age group, gender, region, etc.).

The MarketScan Medicare Supplemental Database contains the healthcare experience of individuals with Medicare supplemental insurance paid for by employers. Both the Medicare-covered portion of payment (represented as Coordination of Benefits Amount, or COB) and the employer-paid portion are included in this database. The tables that make up the Medicare Supplemental Database are the same as those that make up the Commercial Database.

Claims are not included in the database until they have been adjudicated; there is a lag of approximately six months after the close of a calendar year or a quarter between services provided and their inclusion in the Research Databases. However, the Early View Database has a 90-day lag that includes paid amounts for 100 percent of prescription drugs, approximately 85 percent of physician office visits, and approximately 70 percent of hospital claims. The MarketScan Early View Database includes all of the components found in the standard MarketScan Commercial and Medicare Supplemental Databases. It includes standardized inpatient, outpatient, pharmaceutical, and health-plan enrollment data. The MarketScan Early View Database captures healthcare services incurred up to 90 days before data release and includes only adjudicated claims. However, the medical component of care for some patients will not be complete, since some claims (particularly inpatient claims) take longer to be adjudicated. Because this study is examining only comorbidities prior to and treatments during or prior to tofacitinib initiation fully adjudicated claims are not required and all available data will be used including Commercial, Medicare Supplemental, and Early View Databases.

8.5. Study Size

The sample size for this study is fixed by the duration of the observation window. No formal sample size computation was performed. All patients who meet inclusion/exclusion criteria will be included in the analyses.

8.6. Data Management

All data is electronically obtained from the US Claims databases and delivered to Pfizer. The data are stored in the Real World Data and Analysis DataMart (Teradata Server Version 15). Analysis is done using SAS Version 9.4 on Red Hat Linux.

8.7. Data Analysis

8.7.1. Primary Objectives

8.7.1.1. To Compare 12-month Post-Index Medication Persistence Duration (days) by TOFA Index Prescription OOP Costs and TNFi Cycling with ETN and ADA vs. TOFA Switching

For this objective both descriptive and multivariable analysis will be conducted. For the descriptive analysis, treatment persistence duration (days) with index medication at 12-months will be compared for those with low (\leq median) vs. high (> median) OOP costs and for those who switch from ADA to ETN vs. ADA to TOFA and ETN to ADA vs. ETN to TOFA.

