In addition to step edits and prior authorization, another barrier to receiving advanced therapy for RA is the increased out-of-pocket (OOP) cost sharing for patients. An analysis of claims data for over 40,000 RA patients starting bDMARDs between 01/2004 and 12/2013 found that the average cost per prescription remained relatively unchanged, at approximately \$2300 per prescription, while OOP expenditures increased from \$36 (2.5%) per prescription to \$128 (7%).⁸ An analysis of insurance claims data for Medicare Advantage Part D patients with RA found bDMARD prescription abandonment (claim reversal without subsequent fill) ranged from 1.3% for the lowest out-of-pocket (OOP) cost group (\$0-\$250) to 32.7% for the highest OOP cost group (> \$550). Further, the odds of refilling bDMARD therapy were significantly lower for each OOP cost range (\$250.01-\$400.00, \$400.01-\$550.00, and >\$550.00) relative to OOP cost range of \leq \$250.⁹ An analysis of insurance claims for self-insured health plan members with RA starting etanercept or adalimumab demonstrated about 1 week of therapy lost per \$5.50 increase in weekly OOP expenditures. Those with weekly cost >\$50 were 58% more likely to discontinue than patients with lower OOP costs (hazard ratio 1.58, P<0.001).¹⁰ Additionally, Doshi et al¹¹

found using the 5% sample Medicare data that patients with RA belonging to a non-low income subsidy (LIS) group had a higher average OOP cost for Part D bDMARDs of \$484 (29.9% cost sharing) versus \$5 (0.3% cost sharing) in an LIS group which was associated with a 42% lower odds of filling Part D biologic agents while being more than twice as likely to receive Part B biologic agents and having a 31% lower odds of using any biologic agent vs. patients in the LIS group.

The current study is intended to evaluate the impact of restrictions on TOFA including OOP cost sharing and TNFi cycling with adalimumab and etanercept vs. switching to Tofacitinib on treatment persistence, treatment patterns, healthcare resource use, and costs.

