7.1. Primary Objectives

To evaluate the impact of (1a) TOFA index prescription OOP costs and (1b) TNFi cycling with etanercept (ETN) and adalimumab (ADA) vs. switching to TOFA on treatment persistence duration (see Section 8.3).

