Comorbidities of interest	Baseline Characteristic	All	 0/1 flags will be created to identify the presence of the following comorbidities during the 12-month baseline period (see Appendix 4). Cardiovascular diseases. Chronic obstructive pulmonary disease (COPD). Asthma. Kidney disease. Diabetes. Depression. Anxiety. Liver disease. Sleep disorders. Hypertension. Hyperlipidemia. Interstitial lung disease.

Variable	Role	Data source(s)	Operational definition
Cumulative OOP Costs pre-index	Baseline Characteristic	All	The total, pharmacy and medical OOP costs (deductible+copay+coinsurance) resource use from January 1 of index year through Index.
Index Date OOP costs	Baseline Characteristic	All	Total, pharmacy (excluding index medication) and medical OOP costs on index date.
Index Medication (Table	4)		
Index Prescriber	Baseline Characteristic	All	Top 5 index medication prescriber specialties and other or unknown will be identified.
Index month/year	Baseline Characteristic	All	The month and year of the patient's index date (start of TOFA, ETN, ADA) will be identified.
Index Medication OOP costs	Baseline Characteristic	All	The index medication pharmacy OOP costs (deductible+copay+coinsurance) will be identified for the first index medication rx and cumulative by month (1-12) of follow-up (only looking at pharmacy claims here noting index event is a prescription fill).
Index combination vs. monotherapy regimen status	Baseline Characteristic	All	Patients with a use of one of the 4 main NB- DMARDs (injectable and oral MTX, SSZ, HCQ, LEF) within 90 days on or after the index date will be considered as being treated with combination therapy regimen, others will be classified as monotherapy. For monotherapy, will evaluate 6-mos pre-index use of each of the four main and other NB- DMARDs. For combination regiment, will stratify by 6 mos pre-index use of the four main and other NB-DMARDs.
Post-Index Treatment Pa	tterns (Table 4)		
Treatment Persistence (5 groups)	Outcome	All	Persistent with the index medication will be defined as not having a gap in therapy of at least 60 days between fills/admins. For retail pharmacy (rx) claims the day supply will be utilized and rounded to the nearest 28-day supply for ETN and ADA and 30- day supply for TOFA. For subcutaneous ETN and ADA administrations, a 28-day supply will be assumed.

Variable	Role	Data source(s)	Operational definition

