8.7.4. Multivariate Analysis

To control for possible confounding of the relationship between the outcomes and independent variable of interest, select objectives will be conducted utilizing multivariable methods as described above.

Final outcomes for multivariate analysis will be selected after review of descriptive results. Possible outcomes of interest include: total all-cause health care cost, total RA-related health care cost, cost of bDMARDs/tofacitinib/administration/NB-DMARDS, medication effectiveness (yes vs. no).

For each model, specific predictors to be included will be determined based upon clinical rationale and statistical significance. Variables listed in Section 8.3 will be considered for inclusion in the multivariable models. Additional variables identified throughout the course of the study will also be considered. Following standard procedure, regression diagnostics will be performed for each model to assess goodness of fit and violations of model assumptions (eg, multicollinearity, heteroskedasticity). When there are violations of the model, programmers will note them and make appropriate corrections to the data (ie, typically through transformation of either the independent or dependent variables) or in the method of estimation.

In particular, generalized linear models will be fit, using appropriate distributions and links for the nature of the data (eg, normally-distributed data with identity link, binary data and logit link). Results will be displayed on the original scale (that is, the inverse link). If sufficient sample size, tofacitinib IR and tofacitinib XR will be treated as separate groups. That is, contrast statements will be used to average the two groups when comparing to bDMARDs. Point estimates (that is, mean differences, ratios, odds ratios), 95 percent confidence intervals, and p- values will be presented for contrasts; ANOVA table will be presented to display the strength of the independent variables, including point estimates and p-values.

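### The only out-of-pocket cost contrast stated for primary objective 1a is a sample-median split, and the plan does not say how cost enters the promised multivariable model

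*Combined protocol and SAP*

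**What the plan says.** Section 7.1 states the objective without categories: "To evaluate the impact of (1a) TOFA index prescription OOP costs", with persistence duration as the outcome.

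Section 8.7.1.1 opens with "For this objective both descriptive and multivariable analysis will be conducted". For the descriptive part it then says that "treatment persistence duration (days) with index medication at 12-months will be compared for those with low" and high cost, with low meaning at or below the median and high meaning above it. Section 7.2 uses the same grouping for the secondary objectives: "high (>median) vs. low (≤median) TOFA index prescription OOP costs".

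Section 8.3 holds the exposure as a dollar amount per patient (deductible, copay and coinsurance summed), which "will be identified for the first index medication rx and cumulative by month (1-12) of follow-up".

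For the models, section 8.7.4 says that "specific predictors to be included will be determined based upon clinical rationale and statistical significance". It gives no functional form for OOP cost. Its list of possible outcomes, to be settled after the descriptive results are seen, does not include persistence days. Section 8.7.6 adds a logistic model for being persistent at one year, and 8.7.2.2 adds Cox models for time to discontinuation and switching. Neither says how OOP cost is entered.

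Section 6 cites four findings on OOP cost:
- Prescription abandonment "ranged from 1.3% for the lowest out-of-pocket (OOP) cost group" ($0 to $250) to 32.7% in the highest (over $550).
- Refill odds were lower in each of three ranges above $250.
- About one week of therapy was lost per $5.50 rise in weekly cost.
- The hazard ratio for discontinuation was 1.58 above $50 per week.

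**The concern.** The dollar amount is available for every patient, yet the only stated way to use it is as two groups cut at a value that the sample will determine. A patient $1 above the median is treated like the patient who pays most. The contrast cannot return a slope, so it cannot be set beside the per-dollar gradient in section 6. The cut is also tied to none of the dollar thresholds cited there.

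This matters for a primary objective. The sample is fixed by the observation window (section 8.5), so precision lost to the split cannot be recovered with more patients. If the effect lies mainly among the highest payers, a real access barrier could be reported as small. And if the form of OOP cost in the model is chosen only after the median-split table has been seen, the choice is open to being driven by the data.

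**Working it through.** The plan gives no sample size, power or OOP distribution, so there is no figure to reproduce. The distributions and effect shapes below are assumptions, shown over a range.

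**1. Effect linear in cost.** The share of information kept by the split is the squared correlation between the cost term and the indicator of cost above the median. For a normal variable this is 2/π = 0.637, so 1 − 0.637 = 36% is lost and equal precision needs 1/0.637 = 1.57 times the patients. The other rows come from simulation with 2,000,000 draws.

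| Assumed OOP distribution | Kept | Lost |
|---|---|---|
| Normal (or log cost normal, effect linear in log cost) | 64% | 36% |
| Uniform | 75% | 25% |
| Exponential | 48% | 52% |
| Lognormal, log-SD 0.5 / 1.0 / 1.5, effect linear in dollars | 52% / 27% / 9% | 48% / 73% / 91% |
| Two separated clusters | 81% to 92% | 19% to 8% |
| Two equally common copay levels | 100% | about 0% |

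**2. Effect only in the top fraction p of patients (p ≤ 0.5).** All affected patients fall in the upper half, where they make up p/0.5 = 2p of it. The difference between halves is therefore 2p of the true difference. The information kept, relative to a cut at the right place, is p/(1 − p).

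| p | Share of effect shown (2p) | Information kept |
|---|---|---|
| 0.50 | 100% | 100% |
| 0.40 | 80% | 67% |
| 0.25 | 50% | 33% |
| 0.10 | 20% | 11% |

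As an event-count illustration, take the cited hazard ratio of 1.58 as confined to the top 25%, with two-sided 5% and 80% power (both assumed). Events = (1.960 + 0.842)² / [a(1 − a)(ln HR)²], where a is the share of patients in the upper group.
- At the true cut: 7.85 / (0.1875 × 0.209), which rounds up to 201.
- At the median, with ln HR taken as about half (0.229, hazard ratio about 1.26): 7.85 / (0.25 × 0.0523), which rounds up to 601.

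**3. Where the median might fall.** $50 per week is 50 × 30/7 = about $214 per 30 days. For a lognormal cost with mean m and log-SD s, the median is m·exp(−s²/2). The two mean costs cited in section 6 are for other drugs and populations and serve only as a bracket, with s from 0.5 to 1.5.
- Mean $128: the median is $42 to $113, and 10% to 16% of patients exceed $214. Most of the upper half would lie below that threshold.
- Mean $484: the median is $157 to $427, and 42% to 92% exceed $214. The threshold could lie on either side of the median.

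**4. Would a single linear term do better?** Not always. With a true step and cost normal on the modelled scale, a linear term keeps 62% against 67% for the median split if the step is at the top 40%. If the step is at the top 25%, it keeps 54% against 33%. This favours a flexible curve over a straight line.

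**The case against.** The strongest reply is that the split is stated only for the descriptive analysis. Section 8.7.1.1 promises a multivariable analysis in the same paragraph, and 8.7.4 lets any variable in 8.3 be considered, including index OOP cost, which is held as an amount. A reader might infer that objective 1a as a whole is reduced to two groups, and the text does not say so. That part of the reply stands. It does not close the gap, because no section gives any other form for OOP cost and persistence days is not among the listed model outcomes.

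A reader might also infer that at least a third of the information must be lost. The table shows that this is not a lower bound: the loss is 25% for uniform cost and close to nothing for two copay levels, and real copays may well cluster. The largest losses require an effect linear in raw dollars with strongly skewed cost. If the effect is linear in log cost and log cost is normal, the loss returns to 36%.

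Nor do the documents place the effect only among high payers. Two of the findings in section 6 point to high cost, one is a per-dollar gradient and one is graded over ranges. The abandonment figures concern reversed claims with no later fill, whereas cohort entry here requires an index pharmacy claim. The dilution result is therefore an illustration. It also rests on a threshold effect, while the 36% rests on a linear one, so the two should not be added together.

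Finally, part of the objectives is redacted and the draft table workbook is not included, so the point is limited to the visible text.

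**Conclusion.** The point holds as a specification gap in a primary objective. The plan states one form for the exposure, a sample-median split, and leaves open how OOP cost enters the promised model. Used as the estimate for 1a, the split cannot recover the cited gradient and coincides with a cited dollar threshold only by chance. Its cost in information is about 36% under a linear effect with normal cost, more under strong right skew, and less under clustered copays. An effect confined to the top fraction p below one half would appear at 2p of its size. All of these figures depend on an OOP distribution and effect shape that the documents do not give. They do not show that the planned analysis will miss an effect, only that it is a weaker use of data already held.

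**What to change.** In section 8.7.1.1, with a matching sentence in 8.7.4:

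- Name persistence duration as the outcome of the 1a multivariable model, and fit the model within cohorts a and b of inclusion criterion 8.
- Enter index-fill OOP cost as a continuous variable through a restricted cubic spline, for example on log(OOP + 1) with an indicator for $0, with knots fixed in advance.
- Report expected persistence days, and the hazard ratio from a Cox model of the kind already planned in 8.7.2.2, at fixed dollar amounts that include those cited in section 6 ($250, $400, $550, and about $214 per 30 days for $50 per week).
- Keep the median split as the descriptive table, and say whether the median is taken within each cohort or over both.

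No new data are needed. The cost is SAP wording, a model form settled now rather than later, and a curve that takes more words to report than two groups.
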